5.7 Follow-Up

There are six (6) scheduled follow-up visits in this study. Follow-up visits are at following intervals:

- Day 7 (± 2 days)
- Day 14 (± 2 days)
- Day 30 (± 7 days)
- Day 90 (± 14 days)
- Month 6 (± 14 days)
- Month 12 (± 14 days)

Follow-up visits will be scheduled at appointed times after the date of treatment (Index Procedure).

[REDACTED] The Sponsor recognizes that Subjects may not be able to return for follow-up visits on the exact day required, therefore a plus / minus window has been allotted for each visit.

CONFIDENTIAL INFORMATION

[REDACTED] Protocol Template

Revision#: 1

Doc Type: GC

Refer to the Schedule of Events (Section 5.2) for follow-up visit requirements.

CONFIDENTIAL INFORMATION

[REDACTED] Protocol Template

Revision#: 1

Doc Type: GC

5.8 Revisions to the Vascular Access Circuit

Subjects may need revisions to the vascular access circuit (either test / control arm). An appropriate clinical indication (e.g., stenosis, thrombosis, low blood flow, elevated venous pressures, etc.) must be present to trigger a revision to the vascular access circuit.

It is recommended that, when possible, Subjects return to the Investigator for revisions; however, it is understood Subjects may be unable to return to the Investigator for revision procedures. If a revision is not performed by the Investigator, attempts should be made to collect revision data from the facility that performed the procedure. This information can be communicated to the Site via fax, electronic communication, and / or documented phone communication, etc.

5.9 Subject Withdrawal from the Study

The Subject may voluntarily withdraw from the study at any time and should notify the Investigator in this event. The Investigator may also withdraw the Subject from the clinical study at any time based on his / her medical judgment. A Study Completion / Discontinuation CRF should be completed for these Subjects.

5.10 Subject Lost to Follow-Up

The Site will record their documented attempts to schedule follow-up visits with the Subject.

The Subject will be considered lost to follow-up at the end of the study if the Subject does not complete the Month 12 follow up visit. If the Subject is considered lost to follow-up, the last follow-up visit date will be considered their date of discontinuation.

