5.11 Subject Study Completion and Discontinuation

A Study Completion / Discontinuation CRF will be completed for each enrolled Subject at the conclusion of his / her participation in the study. The reason for completion or discontinuation for each Subject should be documented (e.g., Subject completed the study per protocol requirements, expired, vascular graft explanted, or lost to follow-up).

If the Subject expired, the date of death will be recorded. The Investigator will assess whether the death was related to the vascular device, if applicable.

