9.1 Anticipated Adverse Events

Anticipated adverse events are complications that are known to be associated with hemodialysis patients undergoing the creation of vascular graft access. See Section 8, Risk Assessment.

The Sponsor considers occurrences of thrombosis and stenosis to be efficacy outcomes and not adverse events. These occurrences should be reported on a Revision to Circuit CRF.

Should there be clinical sequelae associated with thrombosis and stenosis, these sequelae are considered adverse events and should be reported.

CONFIDENTIAL INFORMATION

[REDACTED] Protocol Template

Revision#: 1

Doc Type: GC

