9.4 Adverse Event Reporting and Coding

AEs will be reported on the appropriate case report form and documented in the Subject's permanent medical record.

The following information on each reported adverse event will be collected:

- Adverse Event Term
- Adverse Event Onset Date
- Relationship
- Severity
- Treatment
- Outcome
- Resolution Date

AEs will be coded using the Medical Dictionary for Regulatory Activities (MedDRA).

AE submission guidelines:

- AE reporting begins once the patient is enrolled in the study. All AEs should be reported from enrollment (study procedure) through study completion / discontinuation.
- Provide a diagnosis if possible. If unable to provide a diagnosis, report the symptoms as separate events. AEs should be reported using the full name without abbreviations or narratives.
- AEs with an outcome status of "Ongoing" should be assessed at each follow-up evaluation to determine if the event has resolved. AEs ongoing at study completion / discontinuation should be completed as "Ongoing" on the AE CRF.

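### Back-dating a lost subject's discontinuation to the last visit puts later adverse events outside the AE reporting window, even when the Site knows of them

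*Protocol*

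**What the plan says.** Four parts of the protocol bear on this.

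- **Lost status and its date (5.10).** A subject is classed as "lost to follow-up at the end of the study if the Subject does not complete the Month 12 follow up visit". The date is then fixed backwards in time: "If the Subject is considered lost to follow-up, the last follow-up visit date will be considered their date of discontinuation".
- **AE window (9.4).** "All AEs should be reported from enrollment (study procedure) through study completion / discontinuation".
- **Thrombosis and stenosis (9.1, repeated in SAP 5.6.1).** The sponsor treats these as efficacy outcomes, not AEs: "These occurrences should be reported on a Revision to Circuit CRF". Their consequences are AEs: "Should there be clinical sequelae associated with thrombosis and stenosis, these sequelae are considered adverse events and should be reported".
- **Revisions done elsewhere (5.8).** If the investigator did not perform the revision, "attempts should be made to collect revision data from the facility that performed the procedure". No visit is needed: "This information can be communicated to the Site via fax, electronic communication, and / or documented phone communication, etc". The section gives no closing date and does not mention discontinuation.

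Protocol 5.11 adds: "A Study Completion / Discontinuation CRF will be completed for each enrolled Subject at the conclusion of his / her participation in the study". It lists death and explantation as reasons separate from loss to follow-up, and the date of death is recorded. The visible SAP text has no rule for events dated after discontinuation and no censoring date. Its endpoint, timing and primary analysis sections are largely redacted.

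**The concern.** Until the study ends, a subject who has stopped attending is not yet lost. AE reporting is open, and the Site is trying to reach the subject and may be receiving revision records from other facilities. When the study ends, 5.10 moves the end of participation back to the last attended visit. A Site applying 9.4 as written then has grounds not to report, or to query, an AE with onset after that visit, even though it is real and known.

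The result depends on attendance. Take two subjects, each hospitalised at Month 9 with sequelae of a graft thrombosis, and both known to the Site. If one attends Month 12, the event is inside the window. If the other was last seen at Month 6 and misses Month 12, it is outside. At stake is the completeness of safety data after Day 90, where AEs and circuit revisions are the visible purposes of the Month 6 and Month 12 visits.

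**Working it through.** The plan gives no figure to reproduce. The check sets the rules side by side and subtracts visit dates.

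**Step 1: when the window closes**

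| Subject | Closing date under 5.10 and 9.4 |
|---|---|
| Completes Month 12 | Study completion |
| Lost | Last attended follow-up visit, assigned only once the study ends |

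**Step 2: which events fall outside, for a lost subject**

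| Event | Position |
|---|---|
| AE with onset on or before the last visit, reported later | Inside the window |
| AE with onset after the last visit | Outside, whether or not the Site knows of it |
| Clinical sequela of thrombosis or stenosis, onset after the last visit | Outside, because 9.1 makes it an AE |
| Thrombosis, stenosis or revision after the last visit | Not settled: 9.1 sends thrombosis and stenosis to the revision form, 9.4 governs AEs, and 5.8 has no end date |
| Death | Need not be back-dated: 5.11 treats it as a separate reason with its own date |

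**Step 3: length of the gap**

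Gap = nominal Month 12 day − day of last attended visit. The schedule is in Protocol 5.7. Assumption: Month 6 = day 183 and Month 12 = day 365.

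- Last seen at Month 6: 365 − 183 = 182 days, about 6 months.
- Last seen at Day 90: 365 − 90 = 275 days, about 9 months.
- Last seen at Day 90 with both ±14-day windows at their extremes: (365 + 14) − (90 − 14) = 379 − 76 = 303 days.
- Last seen at Day 14: 365 − 14 = 351 days.

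**Step 4: number of subjects affected**

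This would need the number randomised, the proportion lost, and the proportion of those with a known AE after the last visit. The first two are redacted where they would be expected and the third is not given, so no count can be derived.

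**Step 5: primary endpoint**

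The antibody endpoint uses samples drawn at the Day 7 and Day 14 visits. A rule about time after the last attended visit does not touch it.

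**The case against.** The strongest reply is that nothing is actually thrown away. A Month 9 AE that the Site hears of at Month 9 concerns a subject who is still enrolled, so 9.4 requires a report at that point. No text tells anyone to delete a report once a discontinuation date is assigned. The sentence in 9.4 is a submission guideline, not an analysis exclusion, and SAP 7.1 and 7.2 plan a table and a listing of all AEs with no visible cut-off. How later events are analysed may be settled in redacted text.

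Much of this stands. A reader might infer that known events are discarded, but the documents do not say so. What remains is that the two protocol rules, taken literally, place such an AE outside the reporting window, and no visible text says what to do with one already reported or learned of late.

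A reader might also infer that revisions at outside facilities are excluded. The text does not support that: no visible passage closes revision reporting at discontinuation or defines an end of observation. The documents only fail to say whether such a revision counts.

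Nor can understated rates or bias between arms be read off the text. If the back-dated date were used for censoring, event-free time would be cut along with events, so the direction is not determined. A difference between arms would need attendance or graft failure to differ. That is possible in a trial where subjects and physicians know the graft type, but it is not shown.

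**Conclusion.** The concern holds for AEs. Sections 5.10 and 9.4 together put AEs with onset after a lost subject's last attended visit outside the reporting window, including sequelae of thrombosis or stenosis and including events the Site knew of before the study ended. For revisions, the finding is only that 5.8 and 5.10 leave their status unclear.

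The stretch of time concerned is about 6 months for a subject last seen at Month 6 and about 9 months if last seen at Day 90, counted to the nominal Month 12 visit with the month lengths assumed above. The share of subjects affected is unknown. A reader might assume that 10–20% are lost and 30% of those have a known later event, giving 0.10 × 0.30 = 3% to 0.20 × 0.30 = 6%. Neither input is in the documents, and reading the product as events lost presupposes that they are dropped, so it is not a result.

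The primary endpoint is untouched. This is a gap in the safety and revision follow-up rules, cheap to close and worth closing. The conclusion rests on the unredacted protocol text; a redacted SAP rule could already settle the analysis side, but the reporting rule would still need correcting.

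**What to change.** In Protocol 5.10 and 9.4:

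1. Keep the last-visit date and the date of last known contact as two separate items.
2. State that, for lost subjects, all AEs and circuit revisions the Site knows to have occurred up to the end of the study are reported and kept in the AE and revision summaries, whatever discontinuation date is assigned.
3. Have Sites record the date and event status of every successful contact, including event-free ones. Section 5.10 currently asks only for documented attempts to schedule visits, which does not establish that a subject was event-free.

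In the SAP, for any rate based on follow-up time, end observation at the last contact at which status was ascertained, with or without an event. Add a sensitivity analysis that censors at the last visit. Observation should not simply run to the latest reported AE or revision, because that would lengthen follow-up only for subjects who had events.

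The cost is a few sentences, a little more data recording at Sites and one extra analysis. Some bias toward observing events will remain if event-free contacts are recorded less often than contacts prompted by an event; the last-visit sensitivity analysis shows how much the choice of end date matters.

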5.11 Subject Study Completion and Discontinuation

A Study Completion / Discontinuation CRF will be completed for each enrolled Subject at the conclusion of his / her participation in the study. The reason for completion or discontinuation for each Subject should be documented (e.g., Subject completed the study per protocol requirements, expired, vascular graft explanted, or lost to follow-up).

If the Subject expired, the date of death will be recorded. The Investigator will assess whether the death was related to the vascular device, if applicable.

5.12 Device Deficiencies

The vascular grafts used in the test arm (GORE® Hybrid Vascular Graft) and control arm are not investigational. Any GORE® Hybrid Vascular Graft deficiencies will be reported through normal product surveillance procedures.

5.13 Explant Procedures

The GORE® Hybrid Vascular Graft may be explanted during a surgical procedure or as part of an autopsy. Sites are requested to return explanted device(s) to the Sponsor for gross and histological evaluation. Prior to planned or potential device retrieval, contact the Gore Associate managing the study to communicate that a specimen is being retrieved from a study Subject. A specimen shipping kit will be immediately sent to the Site. The specimen kit provides specific packaging and handling instructions for the specimen and contains a shipping container.

CONFIDENTIAL INFORMATION

[REDACTED] Protocol Template

Revision#: 1

Doc Type: GC

6. Clinical Study Administration

6.1 Training

Sites selected for this clinical study must be approved to use the GORE® Hybrid Vascular Graft.

6.2 Monitoring

Site monitoring for this study will be provided by [REDACTED]. Monitoring oversight will be provided by the Sponsor.

The Site monitors are qualified by training and experience to oversee the progress of the study at the Site and will ensure that the Investigators and their staff understand and adhere to both the applicable regulatory requirements and the study protocol. In addition, they may assist in resolution of any problems that may arise during the study.

Site Initiation

Site initiation will be performed to assure that each Investigator and his / her staff understands the protocol, applicable regulations, human subject protection requirements, and the Investigator's obligations. This visit will ensure that required training documentation with the appropriate IRB approvals are in place prior to Subject enrollment.

Periodic Site Monitoring

Periodic Site monitoring will occur as necessary to ensure continuing adequacy of facilities and adherence to the clinical study protocol, GCPs, and applicable regulations and laws that pertain to the conduct of the clinical study. These activities will also include the review of CRFs, source documentation, resolution of any missing or inconsistent data, timely submission of accurate records to the Sponsor, and the maintenance of proper records. A report will be written following each Site visit and a follow-up letter will be provided to the Site with a summary of findings. Each Site will also be visited at close-out to ensure all documentation is complete.

6.3 Device Accountability and Storage

The GORE® Hybrid Vascular Graft is a commercially available device and does not require device accountability tracking. As part of procedure data collection, the Investigator will record device lot numbers and catalog numbers on the CRF.

6.4 Central Laboratory

Central laboratory services for this study will be provided by [REDACTED] [REDACTED]. [REDACTED] will provide Sites with kits for collecting and shipping blood and serum samples through Day 90. [REDACTED] will also perform a hematology panel with differential and provide results to the Sites.

CONFIDENTIAL INFORMATION

[REDACTED] Protocol Template

Revision#: 1

Doc Type: GC

6.5 Core Laboratory

Core laboratory services for this study will be provided by [REDACTED] through Day 90. The core laboratory will analyze serum for anti-platelet factor 4/heparin antibodies by EIA-GAM, [REDACTED].

6.6 Protocol Deviations

A protocol deviation is defined as any change, divergence, or departure from the study design or procedures of a research protocol that is under the Investigator's control. The Principal Investigator is responsible for promptly reporting protocol deviations to his or her IRB per IRB policy and the Sponsor. The Sponsor will determine the effect of the protocol deviation on the scientific soundness of the clinical study and Subject safety and determine if additional reports or actions are required. Additional action may include Site retraining and / or Site termination from participation in the trial.

The Investigator will not implement any changes to the protocol without first obtaining written agreement from the Sponsor and documented approval from the IRB except in the event of an immediate hazard(s) to a Subject. The Investigator will report the deviation in accordance with the applicable regulations.

6.7 Clinical Data Review

Clinical data will be reviewed at periodic intervals to ensure consistent and accurate reporting. Cases to be reviewed will include, but will not be limited to, adverse events, protocol deviations, and study procedures. Data will be reviewed by the Clinical Study Team and will include the Sponsor's Product Specialist and at least one medical director.

6.8 Protocol Amendments

The Investigator will obtain IRB approval on all amendments in a timely manner. The Sponsor will ensure proper training of Investigator and Site staff on all protocol amendments.

6.9 Sponsor Representatives

Sponsor field representatives / clinical staff may be present during study procedures to provide technical assistance to the Investigator in the use of the device. The activities of these Sponsor representatives will be supervised by the Investigator to avoid bias, ensure data quality, and protect patient rights.

6.10 Access to Source Data / Documents

Source data are defined as all information necessary for the reconstruction and evaluation of the clinical investigation.

**CONFIDENTIAL INFORMATION**

Protocol Template

Revision#: 1

Doc Type: GC

The Investigator will keep all study records and source data for inspection by the Sponsor, Sponsor's monitors, IRB, and regulatory authorities.

6.11 Study Records Retention

The Investigator will maintain complete, accurate and current study records as required by applicable regulatory requirements. Clinical study records will not be disposed of, nor custody of the records transferred, without prior written Sponsor approval.

Investigator records will include, but not be limited to:

- All correspondence with another investigator, an IRB, the Sponsor, a monitor, a regulatory body, including required reports.
- Records of each Subject's case history and exposure to the device. The case history for each Subject shall document that informed consent was obtained prior to participation in the study. Case histories include the following:
 - Case report forms
 - Signed and dated consent forms and documents evidencing informed consent
 - Medical records (e.g., progress notes of the physician, the Subject's hospital chart(s), and the nurses' notes
 - For any use of a device without informed consent, a written concurrence of a licensed physician and a brief description of the circumstances justifying the failure to obtain the informed consent.
 - All relevant observations, including records and date and condition of each Subject upon entering, and information about relevant previous medical history and the results of all diagnostic tests.
- The protocol, any amendments, and documentation of any deviations from the protocol, including the dates and the reasons for such deviations.
- A certification stating the IRB is in compliance with FDA regulations.
- Any other records as required by the IRB and the Sponsor.

The Investigator will prepare and submit the following reports:

- Withdrawal of IRB approval: The Investigator will report any withdrawal of approval within five working days after the Investigator has been notified of the withdrawal.
- Progress reports: Progress reports documenting the procedure, AEs, and follow-up data concerning individual Subjects will be submitted to the Sponsor on standardized CRFs. The Investigator may also be required to submit progress reports and final reports to the IRB and to the Sponsor summarizing the Investigator's experience during the study.
- Protocol Deviations shall be reported as described in Section 6.6.
- Other: Any other reports as reasonably requested by the Sponsor or required by applicable local regulations.

CONFIDENTIAL INFORMATION

[REDACTED] Protocol Template

Revision#: 1

Doc Type: GC

6.12 Clinical Trial Registration

If applicable, the Sponsor will register the study and post results as required by applicable U.S. laws and regulations.

7. Data Collection and Submission

The Clinical Data Management System (CDMS) for this study will be provided by

7.1 Data Collection Methods

This study will report clinical data using the software utilized by [REDACTED]

The CDMS will be the database of record for the protocol and subject to regulatory inspections. All users will be trained to use the CDMS and will comply with study-specific guidelines / instructions as well as applicable regulatory requirements.

Subject data will be collected using protocol-specific CRFs. Site staff and core laboratory will enter data directly into the CRF for transmission to the Sponsor. The Sites will be notified of any significant amendments to the CRFs.

7.2 Data Clarification and Correction

Once entered, data will be evaluated to ensure it is complete, consistent, and logically sound. If changes to the data in the CDMS are required, all changes, reasons for changes, and persons making the changes will be captured in the CDMS' audit trail.

8. Risk Assessment

8.1 Potential Risks

The risks associated with the GORE® Hybrid Vascular Graft for use in hemodialysis are expected to be similar to the risks associated with the use of non-heparin bonded synthetic vascular grafts.

Risks associated with these devices, including the GORE® Hybrid Vascular Graft, or the surgical procedure include but are not limited to:

CONFIDENTIAL INFORMATION

Protocol Template

Revision#: 1

Review Date:

[REDACTED]	[REDACTED]
[REDACTED]	[REDACTED]
[REDACTED]	[REDACTED]

In comparison to patients receiving standard vascular grafts for hemodialysis, the only additional potential risks to Subjects enrolled in this clinical study are the bioactive heparin on the luminal surface and the insertion of the NRS of the GHVG. All other aspects of the vascular graft are equivalent.

